## 6.4 Treatments Administered – Expansion Phase

An overview of treatments administered for the monotherapy and combination therapy cohorts for Part 2 and Part 3, is provided in [Table 3-3](#). Additional details are provided in the sections below.

### 6.4.1 TTI-621 Monotherapy

#### Phase 1b – Part 2 and Part 3

Subjects enrolled in these cohorts will receive a starting dose of 0.2 mg/kg/week TTI-621. For Part 3, intrasubject TTI-621 dose-intensification is required for newly enrolled subjects. All subjects will receive a dose ramp-up regimen which includes initial two-weeks of 0.2 mg/kg treatment followed by intrasubject dose intensification at an increment of 0.1 mg/kg per week up to 0.5 mg/kg within 5-8 weeks. Details regarding when dose intensification should be delayed or stopped due to AEs are provided in [Section 6.5.3](#).

#### Phase 1b Dose Optimization - Part 4

Subjects in the phase 1b dose optimization phase (Part 4) will undergo dose escalation of TTI-621, starting with Level 1 (dose of 0.5 mg/kg) per dose escalation plan (See [Table 3-4](#), [Section 3.3.2](#)) given once weekly. Following a 3+3 escalation design and using a revised DLT criteria, enrollment will continue through Level 2 (starting dose of 0.7 mg/kg), Level 3 (starting dose of 1.0 mg/kg) and Level 4 (starting dose of 1.4 mg/kg) respectively. In the starting dose cohort (0.5 mg/kg), the first 3 patients will be treated sequentially to allow close monitoring of toxicity and timely dose adjustment if needed. The second and third patient will not start the study treatment until the first and second patient, respectively, have completed the initial 2 weeks of study treatment and had no observation of TEAEs meeting DLT criteria. If a DLT is noted in Level 1, there may be de-escalation to Cohort 0 (priming dose of 0.2 mg/kg at week 1 followed by 0.5 mg/kg at subsequent doses) with progression through Levels 2, 3 and 4 using the dose priming approach of 0.2 mg/kg at week 1 followed by the respective level dose regimens at subsequent weeks.

### 6.4.2 TTI-621 plus Rituximab Combination Cohort

Subjects enrolled in this cohort will receive a starting dose of 0.1 mg/kg TTI-621 in combination with 375 mg/m^2 rituximab given weekly (1 cycle) for up to 8 cycles according to the institutional standard of care. Intrasubject TTI-621 dose-

intensification is required for newly enrolled subjects as outlined in [Section 6.5.4](#). Subjects who complete 8 cycles of combination therapy or those who have unacceptable toxicity to the combination therapy prior to completion of 8 cycles may continue to receive TTI-621 as a single agent.

All subjects receiving the TTI-621 plus rituximab combination will have previously received rituximab and are thus less likely to experience the typical “first dose” infusion reactions upon re-exposure to rituximab. For subjects in this combination cohort, if rituximab is given on the same day as TTI-621, at least 60 minutes must elapse between completion of the rituximab infusion and initiation of the TTI-621 infusion. Rituximab may also be given the day before TTI-621 infusion, particularly for subjects who have a history of Grade 2 or 3 rituximab infusion-related reactions. Any rituximab infusion-related reactions must be Grade 2 or lower and have fully resolved to initiate the TTI-621 infusion on the same day. Any rituximab infusion-related reactions that do not meet these criteria must be discussed with the Medical Monitor to determine optimal next steps. Subjects who have had a prior Grade 4 rituximab infusion reaction will not be included in the combination TTI-621 plus rituximab cohort.

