***Phase 1a Escalation (completed, as of amendment 9)***

A minimum of 3 subjects will be treated in each cohort in a conventional 3 + 3 design, starting at Cohort 1. Given the potential risk for cytokine release syndrome, the first subject in each dosing cohort will be treated and observed for 72 hours before the next subject can receive their first infusion of TTI-621. (Cohort 0 represents a contingency de-escalation dose level in the event that tolerance issues are encountered in Cohort 1). Subjects will receive TTI-621 at the assigned dose once weekly for 3 weeks of treatment/observation for DLT assessment as defined in the protocol. If DLT is encountered in 1 of 3 subjects within a particular cohort, 3 additional subjects will be treated at that dose level. Otherwise,

enrollment will proceed sequentially through the predefined cohorts. Based on the incidence of DLT, the MTD will be determined.

*Phase 1b Expansion (ongoing, as of amendment 9)*

In the expansion phase of the study (Part 2), the safety and preliminary anti-tumor activity of TTI-621 monotherapy at the recommended dose of TTI-621 as identified in the escalation phase were explored in up to 40 subjects per cohort type, as outlined in the table below. These cohorts included: indolent B-cell lymphoma (IBCL), aggressive B-cell lymphoma (ABCL), T-cell lymphoma (TCL), Hodgkin lymphoma (HL), chronic lymphocytic leukemia (CLL), multiple myeloma (MM), acute myeloid leukemia (AML), acute lymphoblastic leukemia (ALL), myelodysplastic syndrome (MDS), myeloproliferative neoplasms (MPN), and small cell lung cancer (SCLC). A cohort of subjects with CD20-positive malignancies were enrolled and treated with TTI-621 in combination with rituximab. In addition, a cohort of subjects with classic HL (cHL) were treated with TTI-621 in combination with nivolumab. Intrasubject dose-intensification after initial exposure to the recommended dose from phase 1a may be permitted at investigator discretion during the course of the study.

An overview of monotherapy and combination treatments administered in the expansion phase (Part 2 and 3) is provided in the table below. Starting doses of TTI-621 are shown; intrasubject dose-intensification may be permitted as outlined in Section 6.5.4.

As of Amendment 9:

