**Dose expansion:**

**Part 2**

- The following monotherapy cohorts are closed to future enrollment: IBCL, ABCL, HL, CLL, MDS, MPN, SCLC, AML, MM, TCL and ALL
- The cohorts with TTI-621 in combination with rituximab or nivolumab for subjects with CD20+ malignancies, and cHL, respectively, will remain open for enrollment until the planned slots are filled

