Seven subjects were subsequently enrolled in Cohort 2a, 6 of whom were DLT evaluable. One of the 6 DLT-evaluable subjects experienced a DLT of Grade 3 hypophosphatemia; therefore, the SRC declared 0.2 mg/kg as the MTD and enrollment to the expansion phase is currently underway. Similarly, a dose of 0.2 mg/kg/week in combination with rituximab was initially recommended for subjects enrolled in the combination treatment arm; however 1 subject treated with TTI-621 experienced an SAE of Grade 3 gastrointestinal bleed; therefore, current subjects receive an initial dose of 0.1 mg/kg TTI-621 administered together with the combination partner agent.

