**Table 6-1: Dose Modifications for Dose 2 and Subsequent Doses**

Clinical Scenario	Action
Grade 3 thrombocytopenia or Grade 4 thrombocytopenia lasting $\leq$ 72 hours*	Continue TTI-621 at the same dose when the re-treatment criterion ( $\geq 75 \times 10^9/L$ or baseline) is met; no dose intensification until no occurrence of the same event at the re-challenge of the same dose (Part 3).
Grade 4 thrombocytopenia (platelet $<25 \times 10^9/L$ ) lasting $>72$ hours* or a platelet count $\leq 10 \times 10^9/L$ at any time	Delay TTI-621 dosing until the re-treatment criterion ( $\geq 75 \times 10^9/L$ or baseline) is met; transfuse platelet prophylactically against bleeding when platelet $<10K$ per ASCO practice guideline; Then resume TTI-621: 
 
• at the same dose if dose delay for 1 week;
 
• at a reduced dose by 1 dose level if dose delay for <math>> 1</math> week;
 
• at a reduced dose by 1 dose level if the event recurs
 
 Dose intensification can occur only when there is no occurrence of the same event upon re-dosing of TTI-621 at the same dose for two consecutive weeks. When dose reduction occurs, no further dose intensification will be allowed (Part 3).
$\geq$ Grade 3 thrombocytopenia (platelet $<50 \times 10^9/L$ ) with clinical bleeding (more than easily controlled epistaxis, mild gum bleeding or menses)	Delay TTI-621 dosing until the re-treatment criterion ( $\geq 75 \times 10^9/L$ or baseline) is met, and then resume TTI-621 at a reduced dose by 1 dose level. No further dose intensification (Part 3) will be allowed.
Grade 4 neutropenia (ANC $<500/\text{mm}^3$ ) lasting $>72$ hours* (unexplained by underlying disease)	Delay TTI-621 dosing when the re-treatment criterion (ANC $>1000/\text{mm}^3$ ) is met then resume TTI-621: 
 
• at the same dose if dose delay for 1 week
 
• at a reduced dose by 1 dose level if dose delay for <math>>1</math> week;
 
• at a reduced dose by 1 dose level if the event recurs
 
 Dose intensification (Part 3) can occur only when there is no occurrence of the same event upon re-dosing of TTI-621 at the same dose for two consecutive weeks. When dose reduction occurs, no further dose intensification will be allowed.

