#### 6.5.4 Intrasubject Dose Intensification (Phase 1b dose expansion Part 3)

For phase 1b Part 3, intrasubject dose intensification will be as follows:

**Newly enrolled subjects:** Dose intensification will start at Week 3 for subjects when the prior TTI-621 dose was associated with Grade 2 or lower treatment-related AEs. From Week 3 to Week 8, subsequent weekly doses of TTI-621 will be increased in 0.1 mg/kg/week increments as tolerated (Grade 2 or lower treatment-related AEs) and not to exceed a maximum dose of 0.5 mg/kg/week. After Week 9, additional dose intensification is not permitted.

**Previously enrolled subjects:** For previously enrolled subjects, dose intensification up to a maximum of 0.5 mg/kg/ week is at the investigator's discretion and should start at Week 3 if the prior TTI-621 dose was associated with Grade 2 or lower treatment-related AEs. More guidance on when to dose intensify in occurrence of AEs is provided in Table 6-1.

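### The protocol conflicts on whether TTI-621 intensification is required in the rituximab and nivolumab cohorts, and leaves unclear whether the Part 3 intensification rules, holds and extra assessments cover them

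*Protocol*

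**What the plan says.** **Where the cohorts sit.** The synopsis lists them under Part 2: "The cohorts with TTI-621 in combination with rituximab or nivolumab for subjects with CD20+ malignancies, and cHL, respectively, will remain open for enrollment". Protocol Section 3.1 and SAP Section 1.2.3 also describe them as Part 2.

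**Starting dose.** Section 1.7 records that "a dose of 0.2 mg/kg/week in combination with rituximab was initially recommended for subjects enrolled in the combination treatment arm". It continues: "1 subject treated with TTI-621 experienced an SAE of Grade 3 gastrointestinal bleed; therefore, current subjects receive an initial dose of 0.1 mg/kg TTI-621".

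**Whether to intensify.** Section 6.4.2 says that TTI-621 "intensification is required for newly enrolled subjects as outlined in" Section 6.5.4, and Section 6.4.3 says the same for nivolumab. The synopsis expansion table answers yes for both cohorts in its mandatory-intensification column. The text before Table 3-3 in Section 3.3.1 also calls it required. The synopsis sentence that introduces the expansion table says instead that it may be permitted. A separate synopsis sentence, about subjects first exposed to the phase 1a recommended dose, says intensification "may be permitted at investigator discretion during the course of the study". Section 1.8.3 says that in Part 2 it became permissible at investigator's discretion.

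**The rules cited.** Section 6.5.4 carries Part 3 in its title and opens: "For phase 1b Part 3, intrasubject dose intensification will be as follows". Table 6-1 attaches the same label to its holds, for example "no dose intensification until no occurrence of the same event at the re-challenge of the same dose (Part 3". The heading of Section 7.6 confines it to Part 3, although its body tells sites how to time assessments in the combination cohorts.

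**The concern.** A site enrolling a new combination subject is told to intensify by reference to a section written for a different part of the study, after a synopsis that calls the step optional. Two questions stay open: must the dose be raised, and if so, do the holds in Table 6-1 and the additional checks in Section 7.6 apply? Those checks include hematology and chemistry 4 hours after the start of the infusion. Read literally, subjects could be stepped up without them.

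This bears first on safety in cohorts still open to enrollment. It also bears on interpretation. Evaluating TTI-621 in combination is a stated objective of Parts 2 and 3, and SAP Section 3.5 summarises Part 2 safety by monotherapy or combination therapy. If sites resolve the conflict differently, the combination summary pools different regimens.

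**Working it through.** **1. Required or optional**

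| Place in the protocol | Status for the combination cohorts |
|---|---|
| Sections 6.4.2 and 6.4.3 | Required, newly enrolled subjects |
| Synopsis expansion table | Mandatory: yes, both cohorts |
| Section 3.3.1, text before Table 3-3 | Required |
| Synopsis sentence introducing the expansion table | May be permitted |
| Section 1.8.3 (Part 2 in general) | Investigator's discretion |

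The synopsis sentence and the one before Table 3-3 do the same job for the same cohorts but use opposite verbs.

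**2. Do the rules reach Part 2?**

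- The opening of Section 6.5 applies it to Parts 2, 3 and 4, subject to exceptions noted in place. Untagged material therefore covers the combination cohorts: delays, reductions, retreatment criteria, and the bar on re-escalation after a toxicity reduction.
- Section 6.5.4 and the intensification clauses of Table 6-1 do note an exception, because they are labelled Part 3.
- Section 7.6 points both ways. Its heading limits it to Part 3, and Sections 7.5, 7.7 and 7.8 send sites to it for Part 3 only. Its body nevertheless addresses combination subjects. Appendix D Table 1 is also mixed: its title covers Parts 2 and 3, but its intensification weeks are labelled Part 3.

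**3. What the ramp gives if it applies**

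Inputs from Section 6.5.4: starting dose s in Weeks 1 and 2, one step of 0.1 mg/kg per week in Weeks 3 to 8, ceiling 0.5 mg/kg. With h held steps, the ceiling is first reached in week

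2 + (0.5 − s)/0.1 + h, provided this is no later than Week 8.

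*Check against the plan's own figure.* For monotherapy, s = 0.2 and h = 0, so 2 + 3 = Week 5. This agrees with the 5 to 8 weeks stated in Section 6.4.1.

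*Combination start.* For s = 0.1 and h = 0, 2 + 4 = Week 6:

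| Week | 1 | 2 | 3 | 4 | 5 | 6 | 7 | 8 |
|---|---|---|---|---|---|---|---|---|
| mg/kg | 0.1 | 0.1 | 0.2 | 0.3 | 0.4 | 0.5 | 0.5 | 0.5 |

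One held step moves the ceiling to Week 7, and two move it to Week 8. With three, the Week 8 dose is 0.1 + 0.1 × (6 − 3) = 0.4.

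**4. Overlap with rituximab**

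Rituximab is weekly for up to 8 cycles. Assume it starts in Week 1 and no TTI-621 step is held:

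| Cycles given | Highest concurrent TTI-621 dose (mg/kg) | Weeks at 0.2 or more | Weeks at 0.5 |
|---|---|---|---|
| 4 | 0.3 | 2 | 0 |
| 5 | 0.4 | 3 | 0 |
| 6 | 0.5 | 4 | 1 |
| 7 | 0.5 | 5 | 2 |
| 8 | 0.5 | 6 | 3 |

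The dose rationale for the combinations, Section 1.8.2, gives the 0.1 mg/kg start and does not discuss raising it.

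**The case against.** The strongest reply is that this is a labelling slip and the intent is visible. The operative Sections 6.4.2 and 6.4.3, the synopsis table and Section 3.3.1 agree that newly enrolled subjects are intensified. The permissive synopsis sentence defers to Section 6.5.4, which requires intensification for newly enrolled subjects and leaves it to discretion for those already enrolled; that explains part of the difference in verbs. The cross-reference can be read as importing the Section 6.5.4 conditions: related events after the prior dose no worse than Grade 2, and steps only as tolerated. Section 6.5.2 still requires neutrophil and platelet recovery before every dose. SAP Section 3.4 will show weeks at each dose level for escalated subjects, so a mix of regimens would not be wholly hidden.

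Most of this stands, and it limits the point. It does not settle whether the holds and extra assessments labelled Part 3 apply to Part 2 cohorts, and it leaves a synopsis and a rationale that read as optional.

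A reader might go further in several ways that the documents do not support:

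- *That a reduced start followed by a step-up is itself a contradiction.* It is not. Section 1.7 lowers the initial dose, and Section 3.1 explains gated intensification by attenuation of thrombocytopenia with repeat dosing.
- *That the bleed occurred at 0.2 mg/kg.* Section 1.7 says only that "1 subject treated with TTI-621 experienced an SAE of Grade 3 gastrointestinal bleed"; the dose is implied, not stated.
- *That subjects must reach 0.5 mg/kg.* That dose is a ceiling, approached as tolerated.
- *That the synopsis treatment procedures and Section 3.1 confine the requirement to Part 3.* They state it for Part 3 without excluding other parts.
- *That the 0.5 mg/kg platelet data in T-cell lymphoma were offered to justify the combination ramp.* They are cited for the Part 4 starting level and cohorts.
- *That 40 rituximab and 15 nivolumab subjects are affected.* Those are cohort caps. The requirement covers newly enrolled subjects, and the number of open places is not given.

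**Conclusion.** The conflict is real and lies in current text. The protocol both requires and merely permits intensification in the combination cohorts, and it sends them to rules, holds and assessments labelled for another part. The general delay and reduction rules do apply to them; the coverage of the intensification-specific provisions is what remains unclear.

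Its size depends on how far the ramp runs. With every step tolerated, 0.2 mg/kg is reached again at Week 3 and 0.5 mg/kg, five times the start, at Week 6. Reaching 0.5 mg/kg during rituximab needs at least six weekly cycles and, even with all eight, no more than two held steps. These figures assume that the Section 6.5.4 ramp applies, that steps end at Week 8, and that rituximab starts in Week 1. The number of subjects exposed to the ambiguity cannot be derived from the documents.

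This is a fault of scope and consistency with a direct bearing on safety. It does not show that either the lower start or the ramp is wrong.

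**What to change.** Reconcile the synopsis text and expansion table with Sections 1.8.3, 3.3.1, 6.4.2, 6.4.3 and 6.5.4, so that one statement says whether intensification in the two combination cohorts is required, optional or not done. In Section 6.5.4, at each Part 3 tag in Table 6-1, and in the heading of Section 7.6, state explicitly whether these cohorts are covered. Align the Section 7 visit text and Appendix D Table 1 with the answer. Reconcile the statement with the reason for the reduced start in Section 1.7, and address it in Section 1.8.2. Which rule applies is for the sponsor and the SRC to decide.

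The cost is amendment wording and one SRC discussion. Stating the scope requires no added patients and no new procedures beyond those already written.

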#### **6.4.3 TTI-621 plus Nivolumab Combination Cohort**

Subjects enrolled in this cohort will receive a starting dose of 0.1 mg/kg/week TTI-621 in combination with nivolumab at 3mg/kg given every 2 weeks or a fixed dose per current FDA approved package insert for cHL. Intrasubject TTI-621 dose-intensification is required for newly enrolled subjects as outlined in [Section 6.5.4](#). Subjects who have unacceptable toxicity to nivolumab may continue to receive TTI-621 as a single agent.

For subjects in this combination cohort, if nivolumab is given on the same day as TTI-621, at least 60 minutes must elapse between completion of the nivolumab infusion and initiation of the TTI-621 infusion. Nivolumab may also be given the day before TTI-621 infusion. Any nivolumab infusion-related reactions must be Grade 2 or lower and have fully resolved to initiate the TTI-621 infusion on the same day. Any nivolumab infusion-related reactions that do not meet these criteria must be discussed with the Medical Monitor to determine optimal next steps.

## 6.5 Dose Modifications (Amendment 9)

This section below will be used for the entire phase 1b expansion phase per Amendment 9, including both part 2, part 3 and the dose optimization phase part 4, except where otherwise noted.

### 6.5.1 General Principles

Patients will be evaluated according to the Schedule of Assessments (See [Appendix D. Table 1](#) and [Appendix D. Table 2](#)) for possible toxicities that may have occurred after the previous dose(s). Toxicities are to be assessed according to the NCI CTCAE version 4.03. All toxicities that occur during the study will be actively managed following the standard of care per local institutional practice unless otherwise specified in the protocol. The investigator should try to the best of his/her ability to assess whether an AE is related or possibly related to study drug, and dosing actions of TTI-621 will then be considered accordingly.

In general, patients who have the TTI-621 dose held due to treatment-related or possibly related AE may resume study drug after resolution of the AE, at the same dose level or at a reduced level (dose reduction) by at least 1 dose level. When a dose reduction occurs, the TTI-621 dose will be reduced to the next lower dose either by following the ramp-up dosing regimen in Part 3 or on the established safe dose during phase 1b dose optimization part 4. If the initial dose adjustment does not provide sufficient relief, the dose of TTI-621 can be further reduced if the investigator considers that the patient is benefiting from study treatment and may benefit at a further dose reduced dose level of TTI-621. When a dose reduction of TTI-621 is required due to toxicity, no dose re-escalation will be permitted. If TTI-621 dosing is delayed for > 21 days for TTI-621-related or possibly related toxicities despite supportive treatment per standard clinical practice or more than 2 dose reductions are required in a patient, the investigator should consider discontinuing the patient from study treatment, unless the investigator, after risk-benefit assessment, considers that the patient may benefit from continued study treatment after resolution of AEs and when the re-treatment criteria are satisfied per [Section 6.5.2](#). The patient will continue to be followed for 30 days after the last administration of TTI-621.

Patients who experience a DLT (during DLT evaluation period) or a DLT-like toxicity within the first 21 days of treatment, generally, require that treatment with TTI-621 be permanently discontinued. The patient will be followed until resolution or stabilization of the event. The investigator and medical monitor will decide on a case-by-case basis if it is in the patients' best interest to continue the study treatment. If continuation of

treatment is in the patients' best interest, the dose of TTI-621 will be reduced by at least 1 dose level upon resumption of treatment following recovery of the toxicity or toxicities to a level that satisfies the retreatment criteria (see [Section 6.5.2](#)). The discussion and decision will be documented.

In managing toxicities, dose modification guidelines should be followed closely. However, based on the evolving safety data of TTI-621 and/or individual patient cases, alternative dose modifications may be recommended after discussion between the investigator and medical monitor to maximize exposure of study treatment while protecting patient safety. In principle, dose modification is only required per guidance as described below when the AE is determined to be related to the study drug. However, when non-study-drug related AEs, in the investigator's assessment, would likely result in a medical condition where continuous dosing would add unwanted physical burden and stress to the patient, temporarily withholding the study drug is allowed. Discussions between the investigator and medical monitor are highly encouraged in these instances.

